#### 8.4 Adverse Events, Serious Adverse Events, and Other Reportable Safety Events

The definitions of an AE or SAE, as well as the method of recording, evaluating, and assessing causality of AE and SAE and the procedures for completing and transmitting AE, SAE, and other reportable safety event reports can be found in Appendix 3.

Adverse events, SAEs, and other reportable safety events will be reported by the participant (or, when appropriate, by a caregiver, surrogate, or the participant's legally authorized representative).

The investigator and any designees are responsible for detecting, documenting, and reporting events that meet the definition of an AE or SAE as well as other reportable safety events. Investigators need to document if an SAE was associated with a medication error, misuse, or abuse.

Investigators remain responsible for following up AEs, SAEs, and other reportable safety events for outcome according to Section 8.4.3. The investigator, who is a qualified physician, will assess events that meet the definition of an AE or SAE as well as other reportable safety events with respect to seriousness, intensity/toxicity, and causality.

# 8.4.1 Time Period and Frequency for Collecting AE, SAE, and Other Reportable Safety Event Information

AEs, SAEs, and other reportable safety events that occur after the participant provides documented informed consent, but before intervention randomization, must be reported by the investigator under any of the following circumstances:

- if the participant is receiving placebo run-in or other run-in treatment,
- if the event causes the participant to be excluded from the study,
- if it is the result of a protocol-specified intervention, including, but not limited to washout or discontinuation of usual therapy, diet, placebo, or a procedure.

From the time of intervention randomization through ~96 days after cessation of intervention, all AEs, SAEs and other reportable safety events must be reported by the investigator

Additionally, any SAE brought to the attention of an investigator any time outside the period specified in the previous paragraph also must be reported immediately to the Sponsor if the event is considered related to study intervention.

Investigators are not obligated to actively seek AEs or SAEs or other reportable safety events in former study participants. However, if the investigator learns of any SAE, including a death, at any time after a participant has been discharged from the study, and the investigator considers the event to be reasonably related to the study intervention or study participation, the investigator must promptly notify the Sponsor.

All initial and follow-up AEs, SAEs, and other reportable safety events will be recorded and reported to the Sponsor or designee within the time frames as indicated in Table 6.

Exception: A positive pregnancy test at the time of initial screening is not a reportable event unless the participant has received study intervention.

08V5WQ

Table 6 Reporting Time Periods and Time Frames for Adverse Events and Other Reportable Safety Events

Type of Event	Reporting Period: Consent to Randomization/ Allocation	Reporting Period: Randomization/ Allocation through Protocol- specified Follow- up Period	Reporting Period: After the Protocol- specified Follow- up Period	Time Frame to Report Event and Follow-up Information to Sponsor
NSAE	Report if:  - due to protocol- specified intervention  - causes exclusion  - participant is receiving placebo run-in or other run- in treatment	Report all	Not required	Per data entry guidelines
SAE	Report if:  - due to protocol- specified intervention  - causes exclusion  - participant is receiving placebo run-in or other run- in treatment	Report all	Report if: - drug/vaccine related. (Follow ongoing to outcome)	Within 24 hours of learning of event
Pregnancy/Lactation Exposure	Report if:  - participant has been exposed to any protocol-specified intervention (eg, procedure, washout, or run-in treatment including placebo run-in)  Exception: A positive pregnancy test at the time of initial screening is not a reportable event.	Report all	Previously reported – Follow to completion/ termination; report outcome	Within 24 hours of learning of event
ECI (require regulatory reporting)	Report if: - due to intervention - causes exclusion	Report - potential DILI - require regulatory reporting	Not required	Within 24 hours of learning of event
ECI (do not require regulatory reporting)	Report if:  - due to intervention  - causes exclusion	Report - non-DILI ECIs and those not requiring regulatory reporting	Not required	Within 5 calendar days of learning of event

Type of Event	Reporting Period: Consent to Randomization/ Allocation	Reporting Period: Randomization/ Allocation through Protocol- specified Follow- up Period	Reporting Period: After the Protocol- specified Follow- up Period	Time Frame to Report Event and Follow-up Information to Sponsor
Cancer	Report if:  - due to intervention  - causes exclusion	Report all	Not required	Within 5 calendar days of learning of event (unless serious)
Overdose	Report if:  - receiving placebo run-in or other run- in medication	Report all	Not required	Within 24 hours of learning of event
DILI=drug-induced liver injury; ECI=event of clinical interest; NSAE=nonserious adverse event; SAE=serious				

DILI=drug-induced liver injury; ECI=event of clinical interest; NSAE=nonserious adverse event; SAE=serious adverse event.

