## **Intervention Groups and Duration:**

Arm Name	Intervention Name	Unit Dose Strength(s)	Dosage Level(s)	Route of Administration	Regimen/ Treatment Period/ Vaccination Regimen	Use
MK-2060	MK-2060	15 mg/mL	30 mg	SC	Part 1: Day 1 Part 2: Days 1, 2, 3, 4, 8, 15, and 22 Part 3: Day 1	Test Product
Placebo	Placebo	Saline	0 mg	SC	Part 1: Day 1 Part 2: Days 1, 2, 3, 4, 8, 15, and 22	Placebo

SC=subcutaneous; USP=United States Pharmacopeia

08V5WO

Placebo SC (0.9% sodium chloride infusion, USP sterile saline)

Total Number of Intervention Groups/Arms	There will be 3 intervention groups.
Duration of Participation  Duration of Participation	Part 1: Each participant will participate in the study for approximately 19 weeks from the time the participant provides documented informed consent through the final contact. After a screening phase of 4 weeks, each participant will receive assigned intervention for approximately 1 day. After the end-of-treatment each participant will be followed for approximately 13 weeks.  Part 2: Each participant will participate in the study for approximately 20 weeks from the time the participant provides documented informed consent through the final contact. After a screening phase of 4 weeks, each participant will receive assigned intervention for approximately 4 weeks (4 consecutive days of loading doses followed by weekly single dose x 3). After the end-of-treatment each participant will be followed for approximately 13 weeks.  Part 3: Each participant will participate in the study for approximately 23 weeks from the time the participant provides documented informed consent through the final contact. After a screening phase of 4 weeks, each participant will receive assigned intervention for approximately 1 day. After the end-of-treatment each
	participant will be followed for approximately 17 weeks.

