MK-2060/Placebo Administration			X	X	X	X	X		X		X											MK-2060/Placebo will be administered SC at Time 0. Refer to Sec. 6.2, 8.1.8 and the Study Pharmacy Manual for additional information on the preparation and administration of the study drug.
Local Injection Site Reaction			X	X	X	X	X	X	X	X	X	X		X								Note: Participants who call the CRU to report an injection site reaction on non-visit days may be asked to return to the CRU as soon as possible for an additional assessment. Sec. 8.3.7.

												Part 2	2									
	≤28	eening 8 days Day 1								Int	terve	ntion	1								Post- study	Notes
Scheduled Timing (Week)	Screening 1	Screening 2 a		We	ek 1		We 2		We 3		W	eek •	4			Pos	st W	eek	4			
Scheduled Timing (Day)			1	2	3	4	8	10	15	17	22	23	26	29	35	42	49	63	81	111	130	
Visit Window (Day)			NA	NA	NA	NA	NA	±1	NA	±1	NA	NA	±1	NA	±2	±2	±2	±2	±3	±3	±7	
AE/SAE Review	X																				X	All NSAEs and SAEs will be recorded up to 144-days postdose (inclusive). Sec. 8.4.
Laboratory Procedures																						
Serum hCG (WOCBP only)	X		X								X										X	Appendices 2 and 8
Serum FSH - (WONCBP only)	X																					Appendices 2, 5, and 8
HIV, Hepatitis B and C screen (per site SOP)	X																					Sec. 5.2, Appendices 2 and 8
Drug and Alcohol Screen (per site SOP)	X		X																			Screening and predose drug/alcohol screen are mandatory (predose drug screen may occur in the evening prior to Day 1 at the time of admission); any additional drug screen is conducted per site SOP. Sec. 8.3.5 and Appendix 2.

												Part 2	2									
	≤28	eening 8 days Day 1								Int	terve	ntion	1								Post- study	Notes
Scheduled Timing (Week)	Screening 1	Screening 2 a		We	ek 1		We 2		We 3		W	eek -	4			Pos	st W	'eek	4			
Scheduled Timing (Day)			1	2	3	4	8	10	15	17	22	23	26	29	35	42	49	63	81	111	130	
Visit Window (Day)			NA	NA	NA	NA	NA	±1	NA	±1	NA	NA	±1	NA	±2	±2	±2	±2	±3	±3	±7	
24-Hour Urine Protein Collection			X																			The 24-hour urine collection will begin the evening before dosing. Sec. 8.3.4, Appendix 2.
24-Hour Urine Creatinine Collection			X																			The 24-hour urine collection will begin the evening before dosing. Sec. 8.3.4, Appendix 2.

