Targeted physical examination																X		X				Sec. 8.3.1, Sec. 8.3.7		
Height	X																					Sec. 8.3.1		
Weight	X																			X		BMI to be taken only at Screening 1. Sec. 8.3.1		
Orthostatic VS (HR, BP)	X		X								X											Sec. 8.3.2.2.		
Semi-recumbent VS (HR, BP)	X		X					-X		X	X		X			X		X	X	X		Day 1 measurements will be at predose, 1- and 12-hours postdose. Sec. 8.3.2		
RR and body temperature	X		X		X			X		X	X		X							X		Sec. 8.3.2.		
12-lead ECG	X		X					X		X	X		X							X		Sec. 8.3.3.		
Standard Meals					X				X													Sec. 5.3.1.		
Domiciling			Х							X												Sec. 8.1.11		
MK-2060/Placebo Administration				X																		MK-2060/Placebo will be administered SC at Time 0. Refer to Sec. 6.2, 8.1.8 and the Study Pharmacy Manual for additional information on the preparation and administration of the study drug.		

Part 3																							
		Scheduled Time  Day 1 (hours post-																					
			Da	y I	(ho		s po	st-		Days													
Scheduled Timing	Screening 1	Screening 2 a	Predose	0	1	4	8	12	2 (D1 24 hrs)	3 (D1 48 hrs)	6 (D1 120 hrs) (±1 Day)	8 (D1 168 hrs)	11 (±1 Day)	14 (±1 Day)	21 (±2 Days)	28 (±3 Days)	42 (±4 Days)	60 (±5 Days)	90 (±5 Days)	120 Poststudy b (±5 Days)	134 Phone Follow-up c (±5 Days)	Notes	
Local Injection Site Reaction					X	X	X		X	X	X	X										Note: Participants who call the CRU to report an injection site reaction on Days 4, 5, and/or 7 may be asked to return to the CRU as soon as possible for an additional assessment. Sec. 8.3.7.	
AE/SAE Review	X	X>															X	All NSAEs and SAEs will be recorded up to 104-days postdose (inclusive). Sec. 8.4					
Laboratory																							
Procedures Serum hCG (WOCBP only)	X		X																	X		Appendices 2 and 8	
Serum FSH - (WONCBP only)	X																					Appendices 2, 5, and 8	
HIV, hepatitis B and C screen (per site SOP)	X																					Sec. 5.2, Appendices 2 and 8	

	1												Part	_								
		Scheduled Time  Day 1 (hours post-																				
			Da	•	(no dos		s pos	st-										]	Days			
Scheduled Timing	Screening 1	Screening 2 a	Predose	0	1	4	8	12	2 (D1 24 hrs)	3 (D1 48 hrs)	6 (D1 120 hrs) (±1 Day)	8 (D1 168 hrs)	11 (±1 Day)	14 (±1 Day)	21 (±2 Days)	28 (±3 Days)	42 (±4 Days)	60 (±5 Days)	90 (±5 Days)	120 Poststudy b (±5 Days)	134 Phone Follow-up c (±5 Days)	Notes

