#### 8.1.9 Discontinuation and Withdrawal

08V5WO

The investigator or study coordinator must notify the Sponsor when a participant has been discontinued/withdrawn from the study. If a participant discontinues for any reason at any time during the course of the study, the participant may be asked to return to the clinic (or be contacted) for a poststudy visit as per the number of days described in Section 1.3 (90 days for Part 1, 130 days for Part 2, and 120 days for Part 3) to have the applicable procedures conducted. However, the investigator may decide to perform the poststudy procedures at the time of discontinuation or as soon as possible after discontinuation. If the poststudy visit occurs prior to the safety follow-up time frame as specified in Section 8.4.1, the investigator should perform a follow-up telephone call at the end of the follow-up period (Section 8.4.1) to confirm if any AEs have occurred since the poststudy clinic visit. Any AEs that are present at the time of discontinuation/withdrawal should be followed in accordance with the safety requirements outlined in Section 8.4.

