#### 8.11.3 Poststudy

Participants will be required to return to clinic approximately 90 days for Part 1, 130 days for Part 2, and 120 days for Part 3 after the last dose of study intervention for the poststudy visit. If the poststudy visit occurs fewer than 90/130/120 days after the last dose of study intervention, a subsequent follow-up telephone call should be made at 90/130/120 days post the last dose of study intervention to determine if any AEs have occurred since the poststudy clinic visit.

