#### 8.11.5 Safety Phone Call Follow-Up

A safety follow-up phone call will be performed approximately 14 days after the poststudy visit (within the visit windows allowed per protocol). The safety follow-up phone call must be performed by appropriately trained study site staff. At the discretion of the investigator an in-person follow-up may be performed. If the initial call is unsuccessful, the study site should

make a total of 3 attempts. All attempts to contact the participants will be recorded in the source documents. The calls will facilitate the collection of relevant safety information. The participant will be interviewed to obtain information relating to AEs and SAEs. All safety information described by the participant must be documented in the source documents.

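### Section 8.4.1 ends AE reporting ~96 days after the last dose in every part. In Part 3 both this limit and the schedule's 104-day note fall before the final visit and call; in Parts 1 and 2 it conflicts with longer schedule notes.

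*Combined protocol and SAP*

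**What the plan says.** Section 8.4.1 gives one reporting window without distinguishing the parts: "From the time of intervention randomization through ~96 days after cessation of intervention, all AEs", SAEs and other reportable events go to the sponsor. Table 6 in the same section adds that, once the follow-up period is over, nonserious AEs need not be reported and SAEs only if drug-related. Table 6 gives no day number for that period.

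The Schedule of Activities (1.3) puts the poststudy visit at Day 90 ±5 in Part 1, Day 130 ±7 in Part 2 and Day 120 ±5 in Part 3. Section 8.11.5 adds one more contact: "A safety follow-up phone call will be performed approximately 14 days after the poststudy visit". The schedule carries its own AE limits. The Part 2 note says "All NSAEs and SAEs will be recorded up to 144-days postdose (inclusive". The Part 1 and Part 3 notes are identical: "All NSAEs and SAEs will be recorded up to 104-days postdose (inclusive". In Part 3 the AE/SAE Review row nevertheless runs to the Day 134 call.

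Two other sections bear on this. Section 8.1.9, on discontinuation, takes its period from 8.4.1: "If the poststudy visit occurs prior to the safety follow-up time frame as specified in Section 8.4.1", a call is due at the end of that period. Section 8.11.3 counts from the last dose: "If the poststudy visit occurs fewer than 90/130/120 days after the last dose of study intervention", a call to ask about AEs is due at that day count.

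**The concern.** AEs and bleeding-related AEs are primary endpoints in every part, and Section 4.2.1.1 counts any sign of bleeding, even where no professional intervention is needed. Most such events would be nonserious, and nonserious events are what Table 6 releases from reporting once the window closes.

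The Part 3 poststudy visit includes a full physical examination, an ECG and safety laboratory tests. A site that applied 8.4.1 or the 104-day note literally would hold that visit, find a new minor bleed or an unrelated SAE, and be under no stated duty to report it. Another site, following the AE/SAE Review row, would report the same event. In Parts 1 and 2 a site has two different limits and nothing that says which governs.

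**Working it through.** **Inputs.** Last dose: Day 1 in Parts 1 and 3, Day 22 in Part 2 (Synopsis and Table 1). Window: 96 days after the last dose (8.4.1). Visits and their windows: Schedule of Activities. Call: visit + 14 days (8.11.5). One convention throughout: study day = dose day + number of days.

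**Step 1. Reproduce the schedule's own AE limits.** Visit + 14 gives:
- Part 1: 90 + 14 = 104; the note says 104.
- Part 2: 130 + 14 = 144; the note says 144.
- Part 3: 120 + 14 = 134; the note says 104.

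The rule reproduces two of the three notes. The Part 3 figure equals the Part 1 figure, which suggests a carry-over; that is an inference.

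**Step 2. Compare the 8.4.1 limit with the final contacts.**

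| | Part 1 | Part 2 | Part 3 |
|---|---|---|---|
| 8.4.1 limit | 1 + 96 = 97 | 22 + 96 = 118 | 1 + 96 = 97 |
| Visit minus limit | 90 − 97 = −7 | 130 − 118 = 12 | 120 − 97 = 23 |
| Earliest visit minus limit | 85 − 97 = −12 | 123 − 118 = 5 | 115 − 97 = 18 |
| Call minus limit | 104 − 97 = 7 | 144 − 118 = 26 | 134 − 97 = 37 |

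A positive value means that the contact falls after reporting has ended. The Part 1 visit is covered; the nominal call falls outside in all three parts.

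**Step 3. Test the schedule notes against the same contacts.** The Part 1 note runs to 1 + 104 = Day 105 and covers the nominal Day 104 call. The Part 2 note, counted from the first dose, runs to 1 + 144 = Day 145 and covers the nominal Day 144 call. The Part 3 note also runs to Day 105, which is 120 − 105 = 15 days before the visit (10 at the earliest, 115 − 105) and 134 − 105 = 29 days before the call.

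**Step 4. Part 2 day count.** Study Day 130 is 130 − 22 = 108 days after the last dose. Section 8.11.3 asks for 130 days after the last dose, which is 22 + 130 = Day 152. On that reading the visit falls 152 − 118 = 34 days after the 8.4.1 limit.

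**Step 5. Cross-check Part 3 with the Synopsis.** It says that each "participant will be followed for approximately 17 weeks": 1 + 17 × 7 = Day 120. Its 23 weeks from consent, less a full 28-day screening, give 23 × 7 − 28 = Day 133. Both agree with the Day 120 visit and Day 134 call, and not with 104.

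**Sensitivity.** If the dose day is counted as day 1 of the period, as the schedule's day labels suggest, the Part 3 gaps in Steps 2 and 3 grow by one day. The conclusion does not change.

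**The case against.** The strongest reply is that sites already have a longer, explicit instruction. Section 8 makes adherence to the schedule mandatory, and the Part 1 and Part 2 notes require all AEs to be recorded through the visit and call. That stands. A reader might infer from 8.4.1 that AE collection simply stops at 96 days throughout the study; the documents do not support this for Parts 1 and 2.

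Nor do they support the inference that late events would actually be lost. The visits and calls exist, the Part 3 review row reaches Day 134, Section 10.3.5 has AE information recorded at each examination, and 8.11.5 requires safety information from the call to be documented. Related SAEs stay reportable without time limit.

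It can also be said that 8.1.9 does little harm after discontinuation, because 8.11.3 and 8.11.5 provide further calls. That stands largely too: the 8.1.9 call is not the only closing contact.

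The Part 2 Synopsis ("Part 2: Each participant will participate in the study for approximately 20 weeks") might be read as yet another AE limit, since 20 × 7 − 28 = Day 112 falls before the earliest visit. It states an approximate length of participation, not a reporting rule, and should not carry weight here.

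Finally, the limit is written as approximate. That could absorb a few days, such as the 5-day gap at the earliest Part 2 visit, but not 23 or 37.

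What remains is Part 3, where 8.4.1 and the note are both short, and an unresolved conflict of limits in Parts 1 and 2.

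**Conclusion.** The inconsistency is real and lies between sections of the current text. It is most serious in Part 3 (about 9 open-label participants), where neither stated day limit reaches the poststudy visit or the call: the shortfalls are about 23 and 37 days under 8.4.1, and 15 and 29 days under the note. In Part 2 the 8.4.1 limit precedes the visit by about 12 days on the schedule's count, or 34 on that of 8.11.3. In Part 1 only the call is affected, by 7 days.

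A reader might go further and infer that the safety conclusions are biased. The documents do not support that: Section 9.6 plans descriptive AE summaries, with about 9 active participants per part, and no decision rule depends on the window. The expected consequence is uneven reporting of late nonserious AEs, including minor bleeds, and of unrelated SAEs.

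The figures assume that ~96 is read as 96 and that nominal visit days are used unless stated. The statement that the Part 2 note covers the visit and call assumes the schedule's day count. The text should be corrected, but the likely effect is modest.

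**What to change.** 1. In 8.4.1, replace the ~96-day limit with: through the safety follow-up phone call (Section 8.11.5). Give no fixed day number, so that the text stays right however Part 2 days are counted. Section 8.1.9 follows by cross-reference. It is worth adding that bringing the poststudy visit forward at discontinuation does not shorten the period.
2. In the Part 3 schedule, change the AE note from 104 to 134 days.
3. State once, and use consistently in the Part 2 AE note, Part 2 footnote b and 8.11.3, whether 130 and 144 are study days (108 and 144 − 22 = 122 days after the Day 22 dose) or days after the last dose (Days 152 and 22 + 144 = 166).

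The 96-day contraception period in Section 5.1 serves a different purpose and can stay. Aligning the Part 2 Synopsis is an optional editorial follow-on: a Day 144 call needs (28 + 144)/7 = 24.6 weeks in total, against the stated 20.

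The cost is wording only. No visit, call or sample is added.

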#### 8.4.2 Method of Detecting AEs, SAEs, and Other Reportable Safety Events

Care will be taken not to introduce bias when detecting AEs and/or SAEs and other reportable safety events. Open-ended and nonleading verbal questioning of the participant is the preferred method to inquire about AE occurrence.

#### 8.4.3 Follow-up of AE, SAE, and Other Reportable Safety Event Information

After the initial AE/SAE report, the investigator is required to proactively follow each participant at subsequent visits/contacts. All AEs, SAEs, and other reportable safety events, including pregnancy and exposure during breastfeeding, ECIs, cancer, and overdose will be followed until resolution, stabilization, until the event is otherwise explained, or the participant is lost to follow-up (as defined in Section 7.3). In addition, the investigator will make every attempt to follow all nonserious AEs that occur in randomized participants for outcome. Further information on follow-up procedures is given in Appendix 3.

